5.1.2 Efficacy Endpoints Based on Monthly Collection

Headache Impact Test (HIT-6)

The scoring of the HIT-6 total score will be performed using the Optum Scoring Software. The HIT-6 total scores ranging from 36 to 78 can be categorized into 4 grades, representing little or no impact (49 or less), some impact (50 to 55), substantial impact (56 to 59), and severe impact (60 to 78) due to headache. Subjects will complete the HIT-6 using the eDiary.

Migraine Functional Impact Questionnaire (MFIQ)

The MFIQ is a self-administered 26-item instrument measuring the impact of migraine on broader functioning including 4 domains, Impact on Physical Functioning (5 items), Impact on Usual Activities (10 items), Impact on Social Functioning (5 items), and Impact on Emotional Functioning (5 items). In addition, there is 1 stand-alone global item assessing the overall impact on usual activities. Subjects respond to items using a 5-point scale assigned scores from 1 to 5, with 5 representing the greatest burden. Each domain scores will be calculated as the sum of the item responses, and the sum will be rescaled to a 0 to 100 scale, with higher scores representing greater burden. The recall period is the past 7 days. Subjects will complete the MFIQ using the eDiary.

Allodynia Symptoms Checklist 12 items (ASC-12)

The ASC-12 is a subject reported outcome measure used to assess the frequency of allodynia symptoms. The checklist will ask subjects to assess how often they experience increased pain or an unpleasant sensation on their skin during their most severe type of headache while engaging in each of the following: combing their hair, pulling their hair back (eg, ponytail), shaving their face, wearing eyeglasses, wearing contact lenses, wearing earrings, wearing a necklace, wearing tight clothing, taking a shower (when the shower water hits their face), resting their face or head on a pillow, exposure to heat (eg, cooking, washing their face with hot water), and exposure to cold (eg, using an ice pack, washing their face with cold water).

The subject answers each question using the following categories: “Does not apply to me”, “Never”, “Rarely”, “Less than half of the time”, “Half the time or more”. Responses to each question are assigned a score. A positive response to answer options 1 to 3 is scored as 0, a positive response to answer option 4 is scored as a 1, and a positive

response to answer option 5 is scored a 2. The final grading is based on the sum of the 12 items. Subjects will complete the ASC-12 using the eDiary.

Migraine Disability Assessment Questionnaire (MIDAS)

The MIDAS Questionnaire is a 5-item self-administered questionnaire that sums the number of productive days lost over the past 3 months in 2 settings: the workplace and the home. The MIDAS also assesses disability in family, social, and leisure activities. The MIDAS score is the sum of missed days due to a headache from paid work, housework, and nonwork (family, social, leisure) activities; and days at paid work or housework where productivity was reduced by at least half. The recall period is 3 months.

The score is categorized into 4 severity grades: grade I = 0 to 5 (defined as minimal or infrequent disability), grade II = 6 to 10 (mild or infrequent disability), grade III = 11 to 20 (moderate disability), and grade IV = 21 and over (severe disability). Two other questions (A and B) are not scored, but were designed to provide the physician with clinically relevant information on headache frequency and pain severity. Subjects will complete the MIDAS using the eDiary.

Generalized Anxiety Disorder 7-item Questionnaire (GAD-7)

The GAD-7 is a self-administered 7-item instrument that uses some of the DSM-V criteria for general anxiety disorder (GAD) to identify probable cases of GAD along with measuring anxiety symptom severity. Responders are asked to rate the frequency of anxiety symptoms in the last 2 weeks on a Likert scale ranging from 0 ('not at all') to 3 ('nearly every day'). Items are summed to provide a total score. Score interpretation is as follows: 1 to 4 minimal symptoms, 5 to 9 mild symptoms, 10 to 14 moderate symptoms, and 15 to 21 severe symptoms. Changes of 5 points or more are clinically meaningful. Subjects will complete the GAD-7 using the eDiary.

Patient Global Impression of Change (PGIC)

The PGIC is a subject-reported outcome that evaluates general aspects of a subject's health and assesses if there has been an improvement or decline in clinical status. The PGIC employs a 7-point Likert scale that ranges from (1) 'Very much improved' to (7) 'Very much worse'. Subjects will complete the PGIC using the eDiary.

American Registry for Migraine Research (ARMR) Sleep Questionnaire

The ARMR sleep questionnaire is a novel self-administered 10-item patient-reported outcome that measures parameters of sleep quantity, sleep quality and daytime sleepiness and their relationship with migraine symptomatology and treatment over a 3-month recall period. Items 1 to 3 of the questionnaire evaluate parameters of sleep quantity as a discrete time variable. Items 4-6 and 8-10 evaluate several behaviors that denote poor sleep quality and excessive daytime sleepiness using a five-level Likert scale that ranges from 'strongly disagree' to 'strongly agree'. For each question, 'not applicable' options are also provided and are not scored. Each item may be scored separately or in combination within the same domain. Item 7 refers to lifetime sleep disorders history and will only be collected at day 1 post randomization visit. Subjects will complete the ARMR sleep questionnaire using the eDiary.

Beck Depression Inventory (BDI)-II

The Beck Depression Inventory (BDI)-II is a 21-item questionnaire that assesses severity of depression. Each item is scored from 0 to 3. The total score is categorized into 4 severity grades: minimal depression (0 – 13), mild depression (14 – 19), moderate depression (20 – 28), and severe depression (29 – 63).

Sites will be able to activate baseline period BDI-II on the eDiary at the end of the subject's baseline period, after at least 28 full calendar days have passed (inclusive of the day the subject was set-up on the eDiary device).

5.1.3 Safety Endpoints

Serious Adverse Event (SAE)

An event categorized as "Adverse Event" on the Events eCRF starting on or after signing of the informed consent and up to the End of Study date with the indicator flag "Serious" equal to "Yes".

Treatment-emergent Adverse Event

An event categorized as "Adverse Event" on the Events eCRF starting on or after first dose of investigational product, as determined by "Did event start before first dose of investigational product" equal to "No" or missing, and up to the End of Study date.

Serious Treatment-emergent Adverse Event

A treatment-emergent adverse event with the indicator flag "Serious" equal to "Yes" on the Events eCRF.

Treatment-emergent Adverse Device Effect

A treatment-emergent adverse event with the indicator flag “Is there a reasonable possibility that the event may have been caused by the investigational device” equal to “Yes” on the Events eCRF.

Treatment-related Treatment-emergent Adverse Event

A treatment-emergent adverse event with the indicator flag “Is there a reasonable possibility that the event may have been caused by Investigational Medicinal Product” equal to “Yes” on the Events eCRF.

5.2 Study Dates

Informed Consent Date

The date on which subject signs the informed consent form.

Date of Device Ready for Entry

The date on which an eDiary device is setup and ready for entry

Randomization (Enrollment) Date in DBTP

Randomization (Enrollment) Date in DBTP is the date on which a subject is assigned to one of the treatments through the Interactive Voice Response System (IVRS) in the DBTP.

First (DBTP) IP Dose Date

The first (DBTP) IP dose date is the date on which a subject is administered the first dose of IP during the DBTP following randomization as recorded on the IP Administration eCRF. The first IP dose date may be the same day or after the randomization date.

Last DBTP IP Dose Date

Last DBTP IP Dose Date is the date on which a subject is administered the last dose of IP during the DBTP as recorded on the IP Administration eCRF.

First OLTP IP Dose Date

The first OLTP IP Dose Date is the date on which a subject is administered the first dose of IP in the OLTP following completion of the DBTP as recorded on the IP Administration eCRF.

Last OLTP IP Dose Date

Last OLTP IP Dose Date is the date on which a subject is administered the last dose of IP during the OLTP as recorded on the IP Administration eCRF.

Last IP Dose Date

Last IP Dose Date is the date on which a subject is administered the last dose of IP, which can be during the DBTP or OLTP, as recorded on the IP Administration eCRF.

End of Study (EOS) Date

End of study (EOS) date is defined as the last date on which the subject participates in the study as recorded on the End of Study eCRF.

Primary Completion Date

The primary completion date is defined as the date when the last subject is assessed or receives an intervention for the final collection of data for the primary endpoint(s), for the purposes of conducting the primary analysis, whether the study concluded as planned in the protocol or was terminated early.

For this study, the primary completion date is the date when the last subject in the nonopioid-treated cohort has completed the assessments for week 24 (month 6) or discontinues study.

5.3 Study Points of Reference

Baseline Assessment

Baseline assessment for the endpoint of the interest is defined as the last non-missing measurement taken or the monthly interval assessed (for endpoints derived from daily eDiary collection) before the first dose of investigational product. In cases where baseline measurements are taken on the same day as IP, it will be assumed that these measurements are taken prior to IP being administered. For subjects who are randomized but not dosed after the randomization, the baseline of the study is defined as the last non-missing measurement prior to or on the date of randomization.

For measurements with multiple individual items, such as MFIQ and ARMR, all individual items from the same set of measurement will be used for analysis.

Pre-OLTP Baseline

Pre-OLTP baseline is defined as the last non-missing measurement for the endpoint of interest taken before the first dose of OLTP IP. In cases where the

measurements are taken on the same day as the first dose of OLTP IP, it will be assumed that these measurements are taken prior to IP being administered. For endpoints derived based on daily eDiary data, the pre-OLTP baseline is the last non-missing monthly measurement before the first dose of OLTP IP.

Study Day 1

Study day 1 is defined as the first IP dose date **regardless on or after randomization date**. For subjects who are randomized but **never received any dose**, the study day 1 is defined as the date of randomization.

Study Day

Study Day is defined as the number of days from study day 1.

Before Study Day 1:

$$\text{Study Day} = (\text{Date of Interest} - \text{Date of Study Day 1})$$

On or after Study Day 1:

$$\text{Study Day} = (\text{Date of Interest} - \text{Date of Study Day 1}) + 1$$

Therefore, the day prior to Study Day 1 is -1.

5.4 Study Time Intervals

5.4.1 Study Periods

The following data will be categorized into treatment periods. Any data occurred after EOS date will not be included in the analysis.

Efficacy Assessments at Scheduled Visits, Vitals

- DBTP: Study Day 1 to minimum (first OL dose date, EOS date)
- OLTP: (First OL dose date + 1) to EOS date

Adverse Events, Concomitant Medications

- DBTP: Study Day 1 to minimum (first OL dose date – 1, EOS date)
- OLTP: First OL dose date to EOS date

5.4.2 Monthly Intervals for Efficacy Endpoints Derived From Daily Diary Collection

The (4-week) monthly intervals for efficacy endpoints derived from daily eDiary collection will be determined based on each subject's monthly IP dosing dates. When an IP is missed, discontinued, or no longer required, a 28-day monthly interval will be used. Any eDiary data occurring after EOS date will not be included in the analysis.

Applicable efficacy endpoints utilizing the monthly intervals in [Table 5-1](#) include:

- Monthly migraine days (MMD)
- Monthly headache days (MHD)
- Monthly migraine-free days
- Monthly opioid/opioid-containing medication days
- Monthly acute headache medication days (AHMD)
- Monthly headache days with at least moderate pain intensity
- Monthly acute migraine-specific medication days
- Monthly average headache pain intensity
- Monthly average MPFID physical impairment domain score
- Monthly average MPFID impact on everyday activities domain score

Table 5-1. Monthly Interval for Efficacy Endpoints Derived From Daily Diary Collection

Study Period	Assessment Timepoint	Monthly Interval	
		Start Date (Day)	End Date (Day)
Baseline Period	Baseline	Device ready for entry date ^d	Day prior to study day 1
Double-blind Treatment Period	Week 4 (Month 1)	Study Day 1	Week 4 dose date – 1 ^b
	Week 8 (Month 2)	Week 4 dose date ^a	Week 8 dose date – 1 ^b
	Week 12 (Month 3)	Week 8 dose date ^a	Week 12 dose date – 1 ^b
	Week 16 (Month 4)	Week 12 dose date ^a	Week 16 dose date – 1 ^b
	Week 20 (Month 5)	Week 16 dose date ^a	Week 20 dose date – 1 ^b
	Week 24 (Month 6)	Week 20 dose date ^a	Week 24 dose date – 1 ^b
Open-label Treatment Period	Week 44 (Month 11)	Week 40 visit date ^c	Week 44 dose date – 1 ^b
	Week 48 (Month 12)	Week 44 dose date ^a	Week 48 dose date – 1 ^b
	Week 52 (Month 13)	Week 48 dose date ^a	Start date (day) + 27

^a Start Date (Day) = End date (day) of previous monthly interval + 1 if IP dose date is not available

^b End Date (Day) = Start date (day) of current monthly interval + 27 if IP dose date is not available

^c eDiary will be re-activated at the week-40 visit **during OLTP** irrespective of IP dose status. **Week 40 visit date will be determined by week 40 dose date. If week 40 dose date is missing, week 40 clinic visit date will be used instead. If dose date or clinic visit date of the week was missing, the target date of the week would be used to determine the start date or end date.**

^d Start Date of baseline period= the first eDiary date If device ready for entry date is not available

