7.4.2 Dosage Adjustments, Delays, Rules for Withholding or Restarting, Permanent Discontinuation

7.4.2.1 Amgen Investigational Product: Erenumab or Matching Placebo

Dose adjustments are not permitted.

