9.1.2 Treatment Period

Visits will occur per the Schedule of Activities ([Table 2-1](#)). The date of the first dose of IP is defined as day 1. All subsequent doses and study visits will be scheduled based on the day 1 date. On-study visits may be completed \pm 3 days of the scheduled visit. Administration of IP is to be administered once every 4 weeks during each visit that it is required.

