MOH (ICHD-3 definition)	Headache occurring on 15 or more days per month in a subject with a pre-existing primary headache and developing as a consequence of regular overuse of acute or symptomatic headache medication (on 10 or more or 15 or more days/month, depending on the medication) for more than 3 months. It usually, but not invariably, resolves after the overuse is stopped. Diagnostic criteria (per ICHD-3): 
 a. Headache occurring on ≥ 15 days per month in a subject with a pre-existing headache disorder b. Regular overuse for > 3 months of 1 or more drugs that can be taken for acute and/or symptomatic treatment of headache c. Not better accounted for by another ICHD-3 diagnosis
MOH (protocol defined)	Mean monthly acute headache medication days over 3 consecutive study months at or above ICHD-3 defined thresholds AND mean monthly qualified headache days of any severity ≥ 14 days over the same consecutive study months
MPFID	Migraine Physical Function Impact Diary
MRI	Magnetic resonance imaging
NCT	National Clinical Trials
NSAID	Nonsteroidal anti-inflammatory drug
OLTP	Open-label treatment period
Opioid medication day	Any day in which an opioid/opioid containing medication was administered
PFS	Prefilled syringe
PGIC	Patient's Global Impression of Change
QM	every 4 weeks (ie, 28 days ± 4)
Randomization	A subject is randomized to a treatment assignment
SAS	Safety analysis set
SC	Subcutaneous
Source Data	Information from an original record or certified copy of the original record containing subject information for use in clinical research. The information may include, but is not limited to, clinical findings, observations, or other activities in a clinical trial necessary for the reconstruction and evaluation of the trial. Source data are contained in source documents (original records or certified copies). (ICH Guideline [E6]). Examples of source data include Subject identification, Randomization identification, and Stratification Value.
Study Day 1	Defined as the first day that protocol-specified investigational product(s)/protocol-required therapies is/are administered to the subject
Study month	generally 4 weeks
TBL	total bilirubin
ULN	upper limit of normal

Approved

Abbreviation or Term	Definition/Explanation
US	United States

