8.3 Handling of Missing and Incomplete Data

Subjects may miss specific data points for a variety of reasons. In general, data could be missing due to a subject's early withdrawal from the study, a missed visit, or inability to evaluate an endpoint at a particular point in time. For this study, efficacy endpoints are clinical outcome assessments (COAs) collected via daily eDiary or monthly assessments at the office visits. Missing COAs with respect to quality-of-life questionnaires (MPFID, HIT-6, MFIQ, MIDAS, Sleep questionnaire, Allodynia symptom checklist, BDI-II, GAD-7 and PGIC) will not be imputed. **Missing items in each eCOA questionnaire will be handled based on the scoring algorithm for each COA.**

Subjects could miss entering several days of data in eDiary within each monthly interval. The calculation of monthly measurements about subjects' migraine and non-migraine headaches will be handled using the following method, also described in [Section 5.1.1](#).

- For each monthly interval with ≥ 14 days of eDiary use:

- Monthly frequency measurements will be prorated to 28-day equivalents. Prorated result does not need to be rounded.
- Monthly average scores will be calculated as the average of observed scores.
- For monthly intervals with < 14 days of eDiary use, all monthly measurements will be set as missing.

Missing safety endpoints will not be imputed **except for partial AE start dates**. Missing or incomplete dates will be listed as reported, except for incomplete start date of an AE or concomitant medication, which will be imputed as follows:

Missing	Imputation	Exception on adverse event start date
Day	01	Default to study day 1 if an adverse event started the same year and month as study day 1 and the flag indicates that the adverse event started on or after the first dose of investigational product on the Events eCRF
Day/Month	01 Jan	Default to study day 1 if an adverse event started the same year as study day 1 and the flag indicates that the adverse event started on or after the first dose of investigational product on the Events eCRF
Day/Month/Year	None	—

Similarly, incomplete dates of HRU will be imputed using the same imputation rule as above.

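### SAP Table 5-1 cuts diary months at actual dose dates, so a dose about 15 or more days late followed by a one-step return to the day-1 calendar turns a fully recorded month into missing data

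*SAP*

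**What the plan says.** In the double-blind rows of SAP Table 5-1, each month begins on one dose date and ends the day before the next. Section 5.4.2 gives the exception: "When an IP is missed, discontinued, or no longer required, a 28-day monthly interval will be used". Notes a and b put this into effect. Without a dose date, the start is the day after the previous month's end, and the end is "Start date (day) of current monthly interval + 27 if IP dose date is not available". Note c, attached to the week 40 open-label row, adds a differently worded fallback: when the dose or visit date of a week is missing, "the target date of the week would be used to determine the start date or end date".

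SAP Section 8.3 sets the minimum amount of data: "For monthly intervals with < 14 days of eDiary use, all monthly measurements will be set as missing". Above that minimum, monthly counts are prorated to 28 days.

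On dosing, Protocol Section 9.1.2 says: "All subsequent doses and study visits will be scheduled based on the day 1 date". Visits have a ±3-day window, and the same section adds: "Administration of IP is to be administered once every 4 weeks during each visit that it is required". Protocol Appendix 1 defines QM as 28 days ±4. The heading of Protocol Section 7.4.2 covers delays, but the text beneath it says only "Dose adjustments are not permitted". Neither document says when a late dose counts as missed, or how dosing resumes after one. The product instruction manual, a separate document that was not available, may do so.

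**The concern.** The 28-day fallback protects a subject whose dose was skipped but not one whose dose was late. The protocol ties later doses to day 1, so after a long delay its scheduling rule takes the lost time out of a later month. Proration copes with unequal months only while at least 14 diary days remain. Below that, a month that was recorded in full is discarded.

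The lost month can be month 4, 5 or 6, which make up the primary endpoint window. What follows depends on a rule that the SAP does not state: how one missing month enters the 3-month mean. Protocol Section 10.2.4 imputes missing monthly measurements as nonresponse for dichotomous endpoints; if one missing month voids the mean, a subject in remission is counted as a nonresponder. SAP Sections 5.6 and 8.3.2 average the available months for change scores and descriptive means; if that is also done here, the subject keeps a value and up to 13 recorded days go unused. The observed-data analysis in Table 9-1 requires all three months, so it leaves the subject out and does not recover the data. The primary estimand applies regardless of adherence, so dose timing alone should not make recorded diary data missing.

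**Working it through.** **Inputs.** Target dose days 1, 29, 57, 85, 113, 141 and 169 (every 4 weeks from day 1, Protocol 9.1.2); visit window ±3 days (same section); boundaries and notes a and b (SAP Table 5-1); 14-day minimum (SAP 8.3).

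**The plan's own figure.** With every dose on target, each month is 28 days (for example 141 − 113), as Section 5.4.2 intends.

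**Formula.** Let a dose be *k* days late and the next dose *d* days off its own target (negative if early). The month before the late dose lasts 28 + *k* days (if it began on target). The month after it lasts 28 − *k* + *d* days.

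**Dosing patterns, days in months 3/4/5/6**

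| Pattern | Months 3/4/5/6 | Under 14 days? |
|---|---|---|
| Week 16 on day 128, week 20 on day 141 | 28/43/13/28 | month 5 |
| Week 12 on day 100, week 16 skipped, week 20 on day 141 | 43/28/13/28 | month 5 |
| Week 12 on day 100, week 16 on day 128, week 20 on day 141 | 43/28/13/28 | month 5 |
| Week 20 on day 156, week 24 open-label dose on day 169 | 28/28/43/13 | month 6 |
| Gradual: weeks 16, 20, 24 on days 128, 149, 169 | 28/43/21/20 | none |
| Gradual: weeks 8, 12, 16, 20 on days 72, 96, 120, 144 (month 2 = 43) | 24/24/24/25 | none |
| All later doses shift: days 100, 128, 156, 184 | 43/28/28/28 | none |
| Week 16 recorded as missed, rest on target | 28/28/28/28 | none |
| Day 128 recorded as week 20, week 16 missed | 28/28/15/41 | none with a full diary |

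In the second pattern the dose gaps are 100 − 57 = 43, 141 − 100 = 41 and 169 − 141 = 28 days, so no two doses are closer than 28 days. Note b ends month 4 on day 127, and month 5 is left with days 128 to 140. If note c's target-date wording were applied to week 16 instead, month 4 would be days 100 to 112, giving 43/13/28/28. One month is lost either way.

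**Threshold.** With diary completion *c*, the month is lost at the smallest *k* for which *c* × (28 − *k* + *d*) < 14. For *d* = 0 and *c* = 1, 28 − *k* < 14 gives *k* = 15. For *c* = 0.9, 28 − *k* < 15.6 gives 13. For *c* = 0.8, 28 − *k* < 17.5 gives 11.

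| Returning dose | 100% diary | 90% | 80% |
|---|---|---|---|
| 3 days early | 12 | 10 | 8 |
| On target | 15 | 13 | 11 |
| 3 days late | 18 | 16 | 14 |

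**Can a site follow both dosing rules after a delay?** The latest in-window next dose comes 28 + 3 − *k* days after the late one. At *k* = 8 that is 23 days, below the 24-day lower limit of QM. From 8 days late, an in-window next dose and QM spacing cannot both be kept.

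**Size.** The documents give no late-dose rate, so the following share is an assumption. Take n = 146 per arm (183 × 0.8), the planning rates 33.1%, 50.5% and 64.1%, and a two-sample test of proportions. This gives 85.8% power for 70 mg, against the stated 85%. Multiply every rate by (1 − *x*), where *x* is the share of responders turned into nonresponders in each arm:

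| *x* | 70 mg power |
|---|---|
| 0 | 85.8% |
| 0.5% | 85.5% |
| 1% | 85.2% |
| 2% | 84.6% |

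Power for 140 mg stays above 99.9% throughout.

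**The case against.** The trigger needs a clear departure from protocol. A 15-day delay is 12 days beyond the visit window, and a direct return then puts two doses 13 days apart, against 28 ±4. The main example also depends on a label: SAP Tables 5-2 and 5-7 place day 128 in the week 20 visit window (128 to 155). A site that recorded the dose as week 20, or week 16 as missed, would lose no month with a full diary. The instruction manual may prescribe exactly that. Finally, counting a responder as a nonresponder depends on a separate gap, and dose-anchored months have the merit of matching the dosing cycle.

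Most of this stands, and it limits the point to a rare sequence. It does not remove it. Tables 5-2 and 5-7 govern questionnaires and vital signs, not dose labels, and the documents give no cut-off at which a late dose becomes missed. Keeping the spacing by skipping the next dose still loses a month. Relabelling day 128 as week 20 leaves 15 days in month 5, which at 90% completion is 13.5 diary days and is also lost.

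A reader might infer that any dose 15 or more days late costs a month once dosing is back on the calendar. That is too strong. Both gradual returns above lose nothing, and a returning dose 3 days late, which the window allows, moves the full-diary threshold to 18 days.

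**Conclusion.** The gap is real, narrow and minor. A month is lost despite a complete diary when three conditions hold: the late dose keeps its nominal visit label; it is about 15 or more days late (12 to 18, depending on where in its window the returning dose falls); and dosing returns to the day-1 calendar in one step, either directly or after a skipped or equally late dose. With an incomplete diary the threshold is lower, down to 8 days at 80% completion with an early returning dose.

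The documents do not support a claim that this threatens the primary result. They give no frequency for such delays and no reason to expect a difference between arms, and the assumed 2% loss costs 1.2 percentage points of 70 mg power (85.8 − 84.6). Nor do they support saying that affected responders will be counted as nonresponders, because the SAP leaves the treatment of one missing month open.

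**What to change.** For the double-blind rows of Table 5-1, amend notes a and b: when a dose date is missing or falls outside the ±3-day window of Protocol 9.1.2, set the boundary at the previous boundary + 28 days; otherwise use the dose date. Every boundary then lies within 3 days of target and every month has 28 ± 6, that is 22 to 34, days. Each pattern above that loses a month becomes 28/28/28/28. The primary window also stays close to weeks 13 through 24, as the endpoint is worded.

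The cost is one SAP footnote change and no new data. There are two downsides. For out-of-window doses the month no longer follows the dosing cycle, and the rule changes abruptly: a dose 3 days late moves the boundary, while one 4 days late does not.
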